The substantial residual risk for cardiovascular disease (CVD) risk that persists in patients with optimal low-density lipoprotein (LDL) cholesterol associates with the atherogenic dyslipidemia and postprandial lipemia, is a significant but clinically neglected CVD risk factor in particular in Type 2 diabetes (T2DM) patients [1]. The well recognized dyslipidemia in people with T2DM consists of high fasting and non-fasting plasma triglycerides (TG), low high-density lipoprotein (HDL) -cholesterol and preponderance of small dense LDL particles nominated as the atherogenic lipid triad. Recent studies consistently show that non-fasting triglyceride values are better associated with CVD risk and death than fasting triglyceride values. In addition, non-fasting triglycerides also predicted stroke risk [2]. Indeed, humans are mostly in a postprandial rather than fasting state and therefore non-fasting TG values reflect more accurately the continuous exposure of arterial wall to triglyceride rich lipoproteins (TRLs) and more importantly, to substantial cholesterol load that these particles deliver. In circulation TRLs undergo lipoprotein lipase (LPL)-induced lipolysis and remodeling with the formation of a spectrum of heterogeneous particles referred as TRL remnant particles with a progressive reduction of particle size that allows particles to penetrate the arterial wall. Although LDL cholesterol is recognized as the most important lipid factor in early stages of atherogenesis, postprandial TRLs may be relevant to later atherometabolic processes. TRL remnants contribute significantly to intimal cholesterol deposition as remnants contain more cholesterol per particle than LDL.

Postprandial lipemia is highly prevalent even in T2DM patients with normal fasting TG concentrations. Intestinal overproduction of chylomicrons (CMs) and the structural protein apolipoprotein (apo)-B48 has been identified as an integral feature of postprandial lipemia in T2DM and insulin resistance [3,4]. Each CM particle contains one apo-B48 molecule that remains the integral part of CM remnant particles during the lipolysis of the particles by LPL. Consequently apo-B48 can be utilized in vivo to track the secretion and metabolic fate of intestinally derived CM particles [5]. CMs contribute significantly but not exclusively to the elevation of postprandial triglyceride levels. Hepatic very low-density lipoprotein (VLDL) particles are quantitatively the major component leading to increased number of remnant particles.

We recently reported that elevation of plasma TG in abdominally obese dyslipidemic subjects at high CVD risk is due to dual metabolic defects; 1. overproduction of VLDL₁ particles linked to increased liver fat and subcutaneous abdominal fat, and 2. impaired catabolic rate of VLDL₁ particles associated with increases of

apo-CIII [6]. Our recent data suggest that the capacity of the lipolytic pathway is a determinant of both fasting and non-fasting triglyceride levels [7]. *Therefore it is clinically important to elucidate the mechanism for delayed postprandial lipemia and the interactions between dysglycemia and dyslipidemia in T2DM subjects.*

Incretins are hormones released from the gut that respond to the ingested nutrients and potentiate glucose-induced insulin secretion from the pancreatic β -cells. The most important incretins are glucagon-like peptide-1 (GLP-1) and glucose-dependent insulinotropic polypeptide (GIP), both of which are rapidly inactivated by the enzyme dipeptidyl peptidase-4 (DPP-4) [8-10]. Incretins are important in the regulation of postprandial glucose levels [11-13]. Importantly the incretin effect is strongly reduced or lost in T2 DM patients. Recently new approaches that targets incretin hormones including the GLP-1 receptor (GLP-1R) agonists and DPP4 inhibitors have been developed with a mechanism of action distinct from existing glucose lowering agents [10,14]. Incretin based therapies with GLP-1 agonists are accepted as an ideal add on therapy to intensify glucose control in combination therapy as they offer benefits like weight loss and no hypoglycemia [15].

[figure not shown]

Figure 1. Coordinated TRL metabolism during the fasting-to-fed transition.

The intestine actively produces chylomicrons and secretes gut hormones, including GLP-1 and GLP-2. A shift of TRL metabolism from fasting to fed state involves 1) dietary fat absorption and chylomicron secretion, 2) decreased adipose tissue lipolysis and free fatty acid (FFA) flux to liver and intestine, with net FA uptake by adipose tissue, 3) increased chylomicron remnant uptake by the liver, 4) fatty acid “spillover” (i.e., FA released by intravascular lipolysis of TRL not taken up and stored in adipose tissue) and utilization for VLDL and possibly chylomicron synthesis, 5) increased hepatic de novo lipogenesis

(DNL), 6) increased liver lipid droplet storage, and 7) relative reduction in fatty acid (FA) oxidation vs. esterification of FA in liver. Altered hormonal secretion plays an important role in coordinating this transition, including glucose and GLP-1-stimulated insulin secretion and suppressed glucagon secretion from the pancreas. GLP-1 suppresses, GLP-2 stimulates, and insulin suppresses intestinal chylomicron secretion, whereas insulin and glucagon suppress hepatic VLDL secretion. The effect of GLP-1 on hepatic VLDL secretion is currently poorly characterized in humans.

Emerging data indicate that incretins modulate not only glucose metabolism but also lipid metabolism via GLP-1 receptor activation. GLP-1 plays an important role in the assembly and secretion of chylomicrons (Figure 1) [16]. Pharmacological augmentation of GLP-1 receptor signaling by GLP-1 agonists or DPP-4 inhibition reduces intestinal lipoprotein secretion in experimental studies, suggesting that DPP-4 inhibitors may ameliorate dyslipidemia and thus improve cardiovascular risk profile in patients with T2DM. [17].

Recently we reported that alogliptin (DPP-4 inhibitor) therapy over 16 weeks produced significant reductions in postprandial TG and TRL lipoproteins as well as fasting levels of TG, apo-B48 and RLP cholesterol indicating that burden of remnant particles is ameliorated in a randomized double-blind placebo controlled study [18]. Our data are in line with previous studies showing that vildagliptin, sitagliptin as well as exenatide, a GLP-1 agonist, reduces postprandial lipemia in type 2 diabetic patients [19-21]. Recently exenatide was shown acutely to suppress intestinal lipoprotein production [22]. Likewise Liraglutide was reported to reduce postprandial responses of TG and apoB48 after a fat rich meal [23]. However long-term studies are needed to elucidate the lipid effects of incretin-based therapies. Thus, the available data suggest that the incretin-based therapies have a class effect on intestinal lipid metabolism but there may be some difference in the efficacy to modulate lipid metabolism.

Importantly, GLP-1 receptor expression was recently demonstrated in human hepatocytes and GLP-1 treatment reduced VLDL production in mice fed a high-fat diet [24]. We reported that alogliptin not only reduced postprandial VLDL₁ apo-B48 and TG incremental area under curve (iAUC) but also VLDL₁ apo-B100 iAUC. Recently GLP-1 receptor agonists have been reported to decrease hepatic de novo lipogenesis (DNL) linked with reduced VLDL production and hepatic steatosis in two different animal models [25,26].

Furthermore, we showed that vildagliptin reduced remnant-like lipoprotein particles with a concomitant increase in LDL size [27]. These findings suggest an improvement in the metabolism of the TRLs and decrease in atherogenic modification of LDL particles. Today, it is not known if incretin-based therapies improve reduce production rate of large VLDL particles or their clearance in humans.

As abnormal concentrations of blood lipids can result from changes in the production, conversion or clearance of lipoprotein particle, static measurements of lipid levels do not reveal the underlying mechanism of these lipid disorders. Therefore it is necessary to confirm the effects of GLP-1 agonists on the kinetics of TG, apo-B48 and apo-B100 in the postprandial state using stable isotopes concomitantly with quantification of liver fat to demonstrate how GLP-1 system modulates lipoprotein metabolism in T2DM. Kinetic studies in humans provide an important and unique tool to quantitatively elucidate the dynamics of lipid metabolism providing estimates of lipoprotein secretion and clearance underlining the pathophysiology of lipid disorders.

We have established and validated novel gas chromatography/mass spectrometry (GC/MS) methods to analyze the enrichment of combined load of stable isotopes; ²H₅ glycerol, to track enrichments into VLDL-TG, ²H₃leucine incorporated to apo-B48 and apo-B100, ¹³C₄palmitate a to track the contribution of dietary lipids to VLDL triglyceride secretion and ²H₂O heavy water to quantitate DNL in the VLDL particles released by liver (Table 1, Figure 2).

Stable isotopes
²H₅-Glycerol Injected tracer that is esterified to triglycerides in the liver but not the intestine as it lacks glycerol kinase activity. It is thus only incorporated into VLDL–triglycerides.
²H₃-Leucine Injected tracer that is incorporated into apoB100 and apoB48. Chylomicrons secreted from the enterocytes contain apoB48, while VLDL secreted from the liver contain apoB100.
¹³C₄-Palmitate The dietary tracer [1,2,3,4- ¹³ C]-palmitate will be served in the meal to track the contribution of dietary lipids to VLDL–triglyceride secretion.
²H₂O (heavy water) Given orally. Incorporated into all fatty acids. Used to quantify the amount of fatty acids derived from liver de novo lipogenesis into VLDL ₁ and VLDL ₂ .

[figure not shown]

Figure 2. Outline of a kinetic study that includes three major steps: (i) clinical visit protocol, (ii) sample preparation/processing and enrichment analysis by GC/MS, and (iii) mathematical modeling. Subjects ingest heavy water and ¹³C₄-Palmitate and receive infusions of ²H₅-Glycerol and ²H₃-Leucine (Table 1). After GC/MS-detection of stable isotope enrichments in isolated lipoprotein fractions it is possible to mathematically follow the metabolism of both dietary and endogenous derived triglycerides, apoB-100 and apoB-48 and calculate the amount of de novo –lipogenesis in TRL fractions.

In the development of the model we have utilized the data from 5 subjects who have had a kinetic study (1) in the fasting state and (2) repeated together with an oral fat load test. We have established for the first time that our protocol allows us to follow the production, transfer and direct catabolism of hepatic (VLDL₁ and VLDL₂) and intestinal (chylomicrons) lipoprotein particles and triglycerides in vivo, and to elucidate how DNL and dietary lipids contribute to postprandial TRLs. We also have demonstrated that our new non-steady state model allows the mathematical modeling of the data.

RESEARCH HYPOTHESIS

[figure not shown]
The aim of this study is to elucidate the mechanisms underlying the positive effect of incretin therapy on lipoprotein metabolism in type 2 diabetic subjects and for the first time establish the potential effect on liver DNL. Our study design allows differentiating the impact of weight loss dependent and independent effects of liraglutide on lipoprotein and carbohydrate metabolism.

We hypothesize that:

1. Reversal of the incretin defect by liraglutide will result in reduced production and/or improved clearance rate of chylomicrons and remnants
2. GLP-1 receptor activation in the liver will be associated with decreased hepatic DNL, consequently, reduced production of large VLDL₁ particles and decrease in liver fat content.
3. Positive effects of liraglutide on TRL kinetics and liver fat are further potentiated with weight loss.

TREATMENT

The study will be single blinded into two groups matched for age, sex and BMI in order to achieve similar weight loss in liraglutide and placebo arms. In addition to a fixed dose of metformin (2 g/day) and simvastatin (20 mg/day) treatments, patients will be assigned to liraglutide therapy once daily and randomized to liraglutide group with uncontrolled diet or to placebo group with weight loss of 3.0 kg supervised by the study dietician for 4 months (Figure 3). Previous studies in type 2 diabetes show that the average weight loss with liraglutide is 3-3.5 kg and stable weight is achieved within 3-3.5 months (LEAD1-6). The study cohort will comprise male and female (non-fertile or of child-bearing potential using a medically approved birth control method) with T2DM eligible for treatment with metformin or on stable dose of metformin.

INCLUSION CRITERIA

Obese subjects with T2D and a large waist (waist > 88 cm in women and > 92 cm in men, BMI 27–40 kg/m², triglycerides between 1.0 – 4.0 mmol/L and LDL < 4.5 mmol/l) treated with a lifestyle or metformin (any dose) (HbA1c 6.5-9%) and aged 30 – 75 years will be included. Subjects may or may not use statins. **Only subjects who sign an informed consent are included to the study.**

EXCLUSION CRITERIA

- Type 1 diabetes
- Apo E2/2 phenotype
- ALT/AST > 3x ULN
- GFR < 60 ml/min, clinically significant TSH outside normal range
- Lipid-lowering drugs other than statins within 6 months
- Treatment with pioglitazone, insulin, sulphonylureas, gliptines, glinides, SGLT-2 inhibitors or thiazide diuretics (at a dose of > 25 mg / day) within 6 months
- Blood pressure > 160 mmHg systolic and/or > 105 diastolic
- History of pancreatitis or stomach / other major bleeding, thyroid neoplasia, persistent hypothyroidism or persistent hyperthyroidism
- Any medical condition that puts the patient in the risk of dehydration
- Concurrent medical condition that may interfere with the interpretation of efficacy and safety data during the study.
- Females of childbearing potential who are not using adequate contraceptive methods
- Subjects who have experienced side-effects previously from GLP-1 agonists
- Non-compliance or withdrawal of consent
- **Any information or clinical event described in liraglutide SPC that is a contraindication for the use of liraglutide (http://www.ema.europa.eu/docs/en_GB/document_library/EPAR_-_Product_Information/human/001026/WC500050017.pdf)**

WHITHDRAWAL FROM THE STUDY

- Withdrawal of consent
- Clinical information/condition/adverse event that potentially endangers study subject/study results judged by the PI of the study
- **any information or clinical event described in liraglutide SPC that is a contraindication for the use of liraglutide (http://www.ema.europa.eu/docs/en_GB/document_library/EPAR_-_Product_Information/human/001026/WC500050017.pdf)**

Restrictions during the study:

- No aspirin and non-steroidal anti-inflammatory drugs (NSAIDs) within 1 week before heparin tests (LPL / HL) and biopsies
- No alcohol or strenuous exercise within 72 hours of each special test
- Serum amylase and lipase is followed at screening, week 8 and end of liraglutide treatment period or at clinical suspicion of pancreatitis

STUDY VISITS

All subjects will undergo a screening visit. Before screening, the subjects may visit the study center for screening laboratory tests. After giving extensive oral and written information, a written informed consent form will be obtained from the subjects at the first visit before screening procedures. Subjects will be informed on all adverse events related to all the study procedures they will be submitted to both orally and in writing.

Subjects eligible for the study will enter the run-in phase and treated with Metformin 2 g/day and Simvastatin 20 mg/day for 4 weeks. In the treatment period, subjects are randomized to Liraglutide or placebo. To keep subjects blinded, Liraglutide and placebo will be visually identical and be packed. Liraglutide and placebo will be provided by Novo Nordisk A/S. Investigators are not blinded in order to advice subjects

in placebo group to lose weight 3 kg during the study. Dose will be escalated to Liraglutide 0.6 mg / placebo 0.1 ml for one week, Liraglutide 1.2 mg/ placebo 0.2 ml one week and thereafter Liraglutide 1.8 mg / placebo 0.3 ml s.c. daily injections.

Thereafter the baseline visits will include an OGTT, heparin test, non-fasting kinetics and abdominal MRI investigation days. The investigational product (Liraglutide or placebo) will be given to the subjects together with detailed instructions about the usage and storage (**Shelf life 30 months. After first use: 1 month. Storage in a refrigerator (2°C - 8°C). Do not freeze. Store away from the freezer compartment.**) (in +2 - +8 degrees, opened product in +2 - +29 degrees) of the product during these visits. After the study period of total 4 months these investigations are repeated. In addition to the screening visit(s), the subjects will undergo 8 investigational visits. The subjects meet dietician after randomization. The follow-up about weight, diet and possible adverse events takes place with weekly phone calls/e-mail contacts by the study nurse/dietician/doctor. Subjects fill in dietary records for 3 days before and during the investigational drug. At week 8 after initiation of the treatment period a blood sample for safety is drawn, weight is recorded and the patient meets dietician/study nurse if necessary. In case of unsuccessful weight loss, weight loss > 1.5 kg/month or adverse events, an additional visit is arranged. The duration of the study is 1-1.5 month run in and 4 to 4.5 month investigational phase i.e. 5 to 6 months. The subjects will be followed by a phone call/e-mail/visit 2 weeks after the end of the treatment period.

STUDY PROTOCOL: We will combine the novel kinetic protocol developed by us with several advanced analyses to elucidate how incretins modulate postprandial lipidemia and hepatic DNL in T2D subjects. To specifically elucidate the impact of a GLP-1 agonist on postprandial lipid metabolism, we will perform kinetic studies on all study subjects before and after the 4-months intervention with the GLP-1 agonist.

[figure not shown]

Figure 4. Detailed schedule for lipoprotein kinetic assessment. Red dots represent plasma samples for kinetic data (glycerol, leucine and palmitate enrichment in TRL fractions) and green arrows illustrate time-points for plasma incretin (GLP-1, GIP), glucose and insulin sampling.

1. Kinetic study with stable isotopes combined with an oral fat load. This study is based on the novel protocol developed by us (Figure 4). A detailed description of analysis is given in **Appendix A**.

Tracer labelling. On the evening of the first visit, $^2\text{H}_2\text{O}$ (2 g/kg) will be given between 18:00 and 22:00 to assess the contribution of de novo lipogenesis to fatty acids in VLDL (Figure 3). At 8:00 the following morning, the subjects will receive a bolus injection of $^2\text{H}_5$ -glycerol (500 mg) to assess the VLDL-triglyceride kinetics, and a bolus injection of $^2\text{H}_3$ -leucine (7 mg/kg) to assess VLDL-apoB100 and chylomicron-apoB48 kinetics. The fat rich mixed meal (57 g fat, 63 g carbohydrates and 40 g protein, total 934 kcal) with $^{13}\text{C}_4$ -palmitate tracers (1-2 g) is served 2 h after the infusions begins.

Sampling and sample preparation. Blood samples will be taken at frequent time points as indicated by the red dots (Figure 4) and lipoprotein fractions (chylomicrons, VLDL₁ and VLDL₂) will be separated by density gradient ultracentrifugation (DGU). Concentrations of lipids and apolipoproteins (apo-B100, apo-B48) will be measured in whole plasma and in all fractions at each time point.

Quantification of lipoprotein fluxes. Enrichments of isotopes in lipids (TG, FAs) and in apo-B100 and apo-B48 are determined by GC/MS [28] and/or by proteomics [29] at each time point (red dots). Hepatic DNL is calculated from enrichment of deuterated water ingested during the kinetic study at specified time points (0, 4 and 8 hrs.) [30]. We will use a novel multicompartmental model to describe the fluxes of materials combining apoB100 and apoB48 kinetics [7, 28, 29].

2. Determination of liver, subcutaneous and intra-abdominal fat. Using standardized protocols, we will perform a proton magnetic resonance spectroscopy (MRS) to determine liver fat content and magnetic resonance imaging to determine subcutaneous abdominal and intra-abdominal fat. [31]

3. Lipolytic enzymes, advanced lipid analysis, fat biopsies and genetic studies. We will analyze mass and enzyme activity of LPL and hepatic lipase after an injection of 75 IU/kg heparin. RLP-TG and RLP-cholesterol will be measured at 0, 4, and 8 hrs. A fasting sample is obtained for LDL and HDL size determination.

4. Oral glucose tolerance test. An oral glucose tolerance test will be performed as indicated after overnight fast at screening and the end of the 4 months intervention with the GLP-1 agonist. Glucose and insulin will be measured at 0,5,10,30,60,90,120,180 and 240 minutes and modeling of β -cell function is performed [32]. Samples of markers of energy balance (FFA, β -OHB) will be taken at three time-points (0, 4, and 8hrs) after the oral fat load.

OPTIONAL ANALYSES FOR THE FUTURE STUDIES

1. Advanced lipid analysis, fat biopsies and genetic studies

We will also utilize this protocol to collect material for optional analyses in the future not covered by this budget. We will perform lipidomics profiling of plasma and isolated lipoproteins by GC/MS technology to map lipids and proinflammatory lipid intermediates (with collaborators of principal instigators [name] and [name]). We will obtain needle biopsies of subcutaneous abdominal fat after fasting to measure mRNA levels of proinflammatory cytokines and biomarkers and to analyze lipids in adipose tissue. We will also take a blood sample for DNA extraction and identify common single nucleotide polymorphisms in genes that have been verified to play a role in lipid metabolism, insulin resistance, inflammation or oxidative stress

2. Analysis of biomarkers during the oral fat load; apo-CIII, apo-A5, uric acid, inflammatory biomarkers (hsCRP, TNF- α , IL-6, SAA, IL-8, PON, MPO, MCP-1) and PAI-1 at three time-points (0, 4, and 8hrs) after the oral fat load. Spare samples of plasma/serum for future angiopoietin-like protein 4 and other lipid/metabolic parameters is stored at -80 degrees at all time-points during fat rich meal test and OGTT.

3. Analysis of gut microbiome profile and urine microvesicles. Because obesity and diabetes may induce low-grade inflammation and insulin resistance due to changes in gut microbial community, the subjects will also provide a stool sample (using specific tubes and instructions) for analysis of gut microbiota profile before and after liraglutide treatment. A urinary sample for selective purification of nucleic acids and proteins that are potential markers of metabolic state and chronic diseases.

STATISTICAL METHODS AND POWER

The study continues until 13 subjects have completed in both arms. Subjects completing the protocol are included to the statistical analyses. Paired t-test (within group) and ancova (treatment effect) will be used. The number of subjects needed is based on previous studies and are in accordance with a recently published article showing that a 25% difference in VLDL kinetics can be detected with 9 subjects per each group [33].

PRIMARY OBJECTIVE

1) To examine the effect of 16 weeks of treatment with liraglutide on triglycerides (TG) and apoB48 production rates (PR) and/or fractional catabolic rates (FRC) in the lipoprotein fraction chylomicrons ($S_f > 400$) in patients with T2DM treated with metformin. This will be fulfilled by kinetic modeling during a standardized fat-rich mixed-meal test combined with stable isotope administration.

2) To evaluate the for the first time in humans the effect of 16 weeks of treatment with liraglutide compared to baseline on hepatic DNL and liver fat content in patients with T2DM treated with metformin, assessed during a standardized fat-rich mixed meal test.

SECONDARY OBJECTIVES

To evaluate the effect of 16 weeks of treatment with liraglutide compared to baseline in patients with T2DM treated with metformin, assessed during a standardized fat-rich mixed-meal test combined with stable isotope administration on:

- production rates (PR) of TG, apo-B48 and apo-B100 in the lipoprotein fractions VLDL₁ (Sf 60–400) and VLDL₂ (Sf 20–60)
- fractional catabolic rates (FCRs) of TG, ap-B48 and apo-B100 in the lipoprotein fraction VLDL₁ (Sf 60–400) and VLDL₂ (sf 20–60)
- fasting and postprandial serum total TG, total cholesterol, and total apo-B, apo-B48, RLP-chol and RLP-TG, apo-CIII and apo-A5 as well as fasting LDL and HDL size. RLP-chol and RLP-TG are surrogate markers of remnants. Apo-CIII and apo-A5 are key regulators of the lipolytic cascade.
- TRL clearance assessed as effect on post-heparin lipoprotein lipase (LPL) and hepatic lipase (HL) activities. LPL and HL are the key enzymes regulating lipolysis of TRLs and remnant removal by the liver.
- fasting and postprandial glucose, insulin and C-peptide, assessed also during an OGTT.
- fasting visceral and subcutaneous fat depots assessed by MRS in both fasting and in postprandial period.

SAFETY REPORTING

Any adverse events will be reported to Finnish Medicines Agency (FIMEA) according to local procedures. All adverse events will be collected from the first study-related activity (from the signing of the informed consent) and in all following contacts with the study-subject through-out the project. This includes events from the first trial related activity after the subject has signed the informed consent, and until the post treatment follow-up period. The investigators will copy Novo Nordisk Finland Safety department when expediting to FIMEA any serious adverse reactions (SAR) or suspected unexpected serious adverse reactions (SUSAR) which occurred during the use of liraglutide in the study (**appendix B**). ***In addition, all pregnancies in trial subjects occurring during use of a Novo Nordisk Product will be reported to Novo Nordisk.*** The submission to Novo Nordisk Finland will be made within 15 days from the investigator's first knowledge about a valid case.

BUDGET

The study protocol utilizes state-of the art methods to measure the dynamics of postprandial lipemia and extensive and complex assessments (including magnetic resonance imaging/spectroscopy, biochemical and molecular analyses) all of which need to be performed by skilled personnel. We have calculated an overall budget of approximately 574 000€. The budget does not include study medication (liraglutide). The study is financed by an independent grant from Novo Nordisk Ag and by other research grants.

GENERAL CONSIDERATIONS

The clinical part of the study will be conducted in the research facilities of Research Programs' Unit, Diabetes & Obesity, University of Helsinki; Clinical Research Institute, Huch Ltd. Biomedicum Helsinki, Finland. Laboratory work and analysis will be made in Helsinki and Gothenburg centers. The study protocol will be subjected to the consideration of the Medical Ethical committee of the Helsinki University Central Hospital and permission from the Finnish Medicines Agency (Fimea) will be obtained. The study will be conducted according to GCP and GLP standards. The subjects taking part to the study are insured by a patient insurance taken out by the Helsinki University Central Hospital.

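### The two weight-matched arms can isolate only the weight-independent effect of liraglutide, and the objectives, worded against baseline, do not match the planned between-arm ANCOVA

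*Combined protocol and SAP*

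**What the plan says.** The Research Hypothesis section makes a claim about the design: "Our study design allows differentiating the impact of weight loss dependent and independent effects of liraglutide on lipoprotein and carbohydrate metabolism". Its third hypothesis is: "Positive effects of liraglutide on TRL kinetics and liver fat are further potentiated with weight loss".

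The Treatment section describes two arms, matched for age, sex and BMI "in order to achieve similar weight loss in liraglutide and placebo arms". Patients are "randomized to liraglutide group with uncontrolled diet or to placebo group with weight loss of 3.0 kg supervised by the study dietician". The expectation behind the 3.0 kg target is that "the average weight loss with liraglutide is 3-3.5 kg". Study Visits adds that "Investigators are not blinded in order to advice subjects" in the placebo arm on losing 3 kg, and that eligible subjects "will enter the run-in phase and treated with Metformin 2 g/day and Simvastatin 20 mg/day for 4 weeks" before the treatment period.

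Statistical Methods and Power plans 13 completers per arm, paired t-tests within group, and ANCOVA for the treatment effect. No covariate, weight-change term or interaction is named.

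The objectives are worded differently. Primary objective 1 (chylomicron TG and apoB48 kinetics) states no comparator. Primary objective 2 (hepatic DNL and liver fat) and all secondary objectives set 16 weeks of liraglutide against baseline. None mentions placebo, and none mentions weight loss. The Study Protocol section also frames the kinetic work as before and after: "we will perform kinetic studies on all study subjects before and after the 4-months intervention with the GLP-1 agonist".

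**The concern.** Separating weight-dependent from weight-independent effects requires groups that differ in weight loss as well as groups that differ in drug. Here both arms are steered to about the same loss, so randomisation varies the drug (together with the style of diet management) and holds weight loss roughly constant by intent.

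The objectives then point away from the one contrast that randomisation supports. A change from baseline on liraglutide contains drug effect, weight loss and time together. If DNL or liver fat falls on liraglutide, and falls equally on placebo with the same weight loss, an objective worded against baseline is met although the drug added nothing beyond weight loss. Hypothesis 2 attributes these changes to receptor activation in the liver, and a shared change cannot support that.

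**Working it through.** **1. What the arms identify.** Write the mean change as time + drug (L) + weight loss (W) + their interaction (LW). The arms are (liraglutide, weight loss) and (placebo, weight loss).

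- Liraglutide arm, change from baseline: time + L + W + LW.
- Placebo arm, change from baseline: time + W.
- Difference between arms: L + LW, the drug effect at matched weight loss.

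Two cells give a matrix of rank 2 for four parameters. W is never separated from time by randomisation, and L is never separated from LW. The 4-week run-in reduces background drift in the time term but does not remove it. Hypothesis 3 needs different weight loss on the same treatment, and the arms do not supply that.

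**2. What happens if the paired test is used for attribution.** Inputs: n = 13 (Statistical Methods and Power); two-sided 5% level (assumed); the same change d in both arms, in SDs of change (assumed); no added effect of liraglutide.

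Paired t, 12 df, critical value 2.179, noncentrality d × √13:

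| d | Noncentrality | Liraglutide paired test significant |
|---|---|---|
| 0.25 | 0.90 | 13% |
| 0.5 | 1.80 | 38% |
| 0.8 | 2.88 | 75% |

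Simulation with 100,000 trials and a baseline/follow-up correlation of 0.6 (assumed) gave 12.9%, 38.1% and 75.3% for the paired test, and 4.9%, 4.9% and 5.0% for the between-arm ANCOVA.

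**3. How well the weight match can be judged.** The Treatment section implies an expected gap of 3.0 − 3.0 = 0 to 3.5 − 3.0 = 0.5 kg. The plan gives no SD of weight change, so a range is used.

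- Equal SDs of 2, 3 or 4 kg: half-width of the 95% CI = t(24) × SD × √(2/13) = 2.064 × SD × 0.392 = 1.6, 2.4 or 3.2 kg.
- Placebo SD 1 kg because that arm is steered, liraglutide SD 2, 3 or 4 kg (Welch): SE = √((1 + SD²)/13) = 0.62, 0.88 or 1.14; df 17.6, 14.6 or 13.5; half-width 1.3, 1.9 or 2.5 kg.

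Against a 3 kg target, the trial can describe similarity but cannot establish it tightly.

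**4. Precision of the ANCOVA against the paired test.** With equal variances at both times and correlation ρ (assumed), ANCOVA residual SD / SD of change is k = √((1 + ρ)/2). The ratio of CI half-widths is t(23) × √(2/13) × k ÷ (t(12)/√13), with t(23) = 2.069.

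| ρ | k | CI ratio, ANCOVA/paired | Detectable at 80% power (SD of change) |
|---|---|---|---|
| 0.3 | 0.81 | 1.08 | 0.93 |
| 0.5 | 0.87 | 1.16 | 0.99 |
| 0.7 | 0.92 | 1.24 | 1.06 |
| 0.9 | 0.97 | 1.31 | 1.12 |

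The paired test detects 0.85 SD of change at 80% power.

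**5. The plan's own figure.** Its sample-size basis, a 25% difference with 9 per group, cannot be reproduced because no SD, alpha or power is given. Nothing above depends on it.

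**The case against.** The strongest reply is that the methods line already gives the treatment effect to ANCOVA and keeps the paired test for within-group change. On that reading, setting liraglutide against baseline merely defines the outcome as a 16-week change. This stands in part: a reader might infer that the plan never uses its control arm, and the methods line contradicts that. What remains is a conflict between that line and the objectives, with nothing saying which test answers which objective.

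Second, hypothesis 3 could be explored by relating outcome change to weight change. That is correct, so it would be too strong to say that no analysis could address it. Such an analysis is not specified and would be non-randomised, because weight change follows randomisation. It would also be weak: by Fisher's z, one arm of 13 has 80% power only for a correlation of tanh((1.96 + 0.84)/√10) = 0.71 or more.

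Third, a reader might infer that only placebo subjects receive dietary attention. Study Visits provides a dietician meeting after randomisation, weekly contacts about weight and diet, dietary records and a week-8 weight without limiting them to one arm. It also arranges an extra visit when weight loss is unsuccessful or exceeds 1.5 kg/month. The arms still differ in diet management (uncontrolled against supervised loss), but less than the Treatment section alone suggests. No tolerance for the between-arm weight difference is set.

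Fourth, the placebo arm's before-after change does bear on the weight-dependent part. It does so without randomisation, so the design claim needs a qualifier rather than deletion.

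**Conclusion.** The point holds as a mismatch between claim, objectives and design, and it should be corrected. Randomisation supports a statement about the weight-independent effect, conditional on achieved weight losses being similar. It does not support one about the weight-dependent effect or about potentiation.

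The 13%, 38% and 75% are conditional. They apply only if the paired test is used to attribute effects to liraglutide, and they rest on assumed shifts that are equal in both arms. A reader might take them as the trial's false-positive rate, but the documents do not support that, because they plan an ANCOVA and give no size for a shared change. Nor do they say why the placebo arm was included beyond the aim of similar weight loss, so no motive should be read into it. The structural part of the conclusion needs no assumed number.

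**What to change.** 1. In the primary and secondary objectives, name the placebo/weight-loss arm as comparator. Base conclusions about liraglutide, including DNL and liver fat, on the between-arm ANCOVA already planned. Treat within-arm paired t-tests as descriptive.
2. In the Research Hypothesis section, state that the randomised comparison estimates the effect of liraglutide versus placebo at intended similar weight loss, and that evidence on the weight-dependent part is non-randomised before-after evidence.
3. Label hypothesis 3 exploratory and non-randomised.
4. Beside the primary results, report the between-arm difference in weight change from baseline to end of treatment with its 95% CI, and say that similarity is described, not proven.

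No visits, arms or measurements are added. If the paired test was meant to be the inferential analysis, the estimand changes, the CI is 8-31% wider (assumed correlation 0.3-0.9), and the effect detectable with 80% power rises from 0.85 to 0.93-1.12 SD of change. If ANCOVA already carries the treatment effect, no precision is lost. The weight-change CI will be wide either way.
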